8.4.4 Own brand product use

Between PK sessions, subjects are allowed to use their own brand nicotine products after completion of each PK sampling and until 12 hours prior to the next PK session.

The subjects will be asked to bring their own product to the screening visit and report their daily use. A photo of the subject's own product may be taken as reference in order to identify the product before recording in the eCRF. Use of subjects' own products during the study will be reported in the eCRF.

8.4.5 Blood Volume Collected

The total volume of blood withdrawn will be up to 466 mL. A catheter will be used for PK sampling. The total blood collection may be higher if repeat blood samples are required for safety assessments.

A detailed breakdown of the approximated blood volume to be collected per subject is presented in Table 2.

	Male subject	Female subject		
Screening clinical laboratory tests	14 mL	14 mL		
Pre-PK period 1 serum pregnancy test:	-	3.5 mL		
	416 mL	416 mL		
PK blood samples:	(13 samples per period x 4 mL per sample x 8 periods)	(13 samples per period x 4 mL per sample x 8 periods)		
Safety tests during study	36 mL (4 samples of 9 ml each)	36 mL (4 samples of 9 ml each)		
Total blood collection:	466 mL	466 mL		

Table 2. Blood Volume Breakdown

8.4.6 Pharmacokinetic assessments

8.4.6.1 Sample collection and handling

A total of 13 blood samples will be collected (one tube of 4 mL each) in each study period for PK assessments as scheduled in Table 3.

Sample No	Nominal Time* (hours)
01	0.00**
02	0.08 (equivalent to 5 minutes)
03	0.17 (equivalent to 10 minutes)
04	0.33 (equivalent to 20 minutes)
05	0.67 (equivalent to 40 minutes)
06	0.83 (equivalent to 50 minutes)
07	1.00
08	1.08 (equivalent to 65 minutes)
09	1.25 (equivalent to 75 minutes)
10	1.50 (equivalent to 90 minutes)
11	2.00
12	4.00
13	6.00

Table 3. Pharmacokinetic Blood Sampling Schedule

** Nominal times listed are relative to the time of study product administ
 ** Within 5 minutes prior to study product administration

Allowed time frames for sampling: +/- 2min for all timepoints up to and including 120 minutes. +/-5 minutes for the 240 minutes and 360 minutes samples.

Blood samples will be collected into a labeled tube containing the appropriate anticoagulant as specified by the bioanalytical facility. They will be collected from an indwelling cannula (stylet catheter that requires no flushing), which will be placed in the forearm vein of the subject. As an option to the subject, or if judged necessary by the clinical staff, direct venipuncture will be used.

The time of PK blood sample collection will be calculated relative to the time of treatment administration. The actual time of all PK blood draws will be recorded and reported for all subjects. The actual start and end time of product use will also be recorded.

Urine samples will only be collected at screening and prior to the first and second product administration periods. A urine sample will also be collected from female subjects at PK sampling day 8 for a pregnancy test. Nicotine concentrations for PK assessments will be obtained through bioanalysis of the plasma derived from the blood samples drawn during this study, using a validated bioanalytical method.

8.4.6.2 Pharmacokinetic sample processing, storage and shipping

Blood samples for PK determination will be processed, split, stored, and shipped according to the sample processing instructions supplied by the bioanalytical facility.

8.4.7 Laboratory assessments

Laboratory evaluations will be performed as scheduled in Table 1.

The laboratory evaluations to be conducted for this study are presented in Appendix 19.2 Clinical Laboratory Evaluations.

The physician in charge or delegate will assess each abnormal value to determine if it is clinically significant. Post-product administration clinically significant laboratory values will be reported as AEs, if applicable, as judged by the physician in charge or delegate. Verification of collection for all laboratory test panels will be collected in the clinical database.

8.4.8 Clinical safety assessments

Safety assessments will include symptom-oriented physical examination, oral mucosa examination, vital signs, clinical laboratory tests, and AE monitoring. Additional safety measurements may be performed at the discretion of an investigator for reasons related to subject safety.

The physician in charge will be present or available by phone at the clinical site for at least the first 4 hours following each product administration and will remain available at all times throughout the study.

8.4.8.1 Physical Examination

A physical examination will be performed by a medically qualified and licensed individual as scheduled in Table 1.

The physical examination will include a general review of the following body systems (at minimum): head and neck, cardiovascular, respiratory, abdomen, brief neurological and general appearance, unless a symptom-oriented physical exam is indicated.

The physical examination performed at screening will also include a general mouth examination.

8.4.8.2 Vital Signs

Vital signs will be measured as scheduled in Table 1. Vital signs at screening, at admission to the clinical site and prior to each product administration will include blood pressure, pulse rate and body temperature. Vital signs following each product administration will include blood pressure and pulse rate.

8.4.8.3 12-Lead Electrocardiogram

A twelve-lead ECG will be performed at screening as scheduled in Table 1.

8.4.8.4 Oral Mucosa Examination

Examination of the oral mucosa (including local irritancy) will be performed at screening, at admission to the clinical site and during each study period as scheduled in Table 1. The mucosa examination should be performed before product administration and up to 2 hours after product removal as presented in Table 4.

Table 1. Oral Mucosa Examination Schedule

Oral Mucosa Examination - Scheduled Time Points

Prior to product administration

Up to 2 hours post-product removal

8.4.9 Adverse Events

8.4.9.1 Definitions

8.4.9.1.1 Adverse Event (AE)

Any untoward medical occurrence in a patient or clinical study subject related to the study product or not, and which does not necessarily have a causal relationship with this treatment. An AE can therefore be any unfavourable and unintended sign (including an abnormal laboratory finding), symptom or disease temporally associated with the use of a study product, whether or not related to the investigation product.

This includes events related to the study product or any comparator. This also includes events related to the procedures involved in the Clinical Study Protocol.

8.4.9.1.2 Serious Adverse Event (SAE)

An SAE is any untoward medical occurrence that at any dose

- Results in death
- Is life-threatening
- Requires inpatient hospitalisation or prolongation of existing hospitalisation
- Results in persistent or significant disability or incapacity
- Is a congenital anomaly/birth defect Or
- Is regarded as medically important without meeting the above mentioned criteria.

The term life-threatening in the definition of "serious" refers to an event in which the subject was at risk of death at the time of the event; it does not refer to an event which hypothetically might have caused death if it was more severe.

Hospitalisation is defined as an unplanned overnight stay. Note however that the subject must be formally admitted. Waiting in outpatient clinic or emergency room would not count. A hospital stay planned prior signing the Patient Information Consent (PIC) does not count as SAE, nor does staying in hospital for social reasons (e.g. respite care, the fact that there is no-one at home to care for the patient), nor does planned hospital stay required by the study protocol.

Medically important, includes e.g. blood dyscrasias or convulsions that do not require hospitalisation or allergic bronchospasm requiring intensive treatment either at home or in an emergency room.

8.4.9.1.3 Adverse Reaction (AR) or Treatment Emergent AEs (TEAEs).

All noxious and unintended responses to a study product related to any dose administered. The definition also covers study product errors and uses outside what is foreseen in the protocol, including misuse and abuse of the product.

All adverse events judged by either the reporting Principal Investigator (PI) and/or the Sponsor as having a reasonable causal relationship to the study product qualify as adverse reactions or treatment emergent AEs.

8.4.9.1.4 Unexpected Adverse Drug Reaction (UADR)

An adverse reaction, where the nature, or severity is not consistent with the applicable product information i.e., Investigator's Brochure (IB)

8.4.9.1.5 Suspected unexpected serious adverse reaction (SUSAR)

Any adverse reaction that is classed as serious and is suspected to be caused by the study product that is not consistent with the information about the study product in the safety reference document (IB) i.e. it is suspected and unexpected. The clinical study protocol and/or IB should include when necessary a list of known side effects for both study product and comparator (if applicable). This list should be checked for each SAE that occurs in terms of expectedness. If the adverse reaction is not listed as expected or has occurred in a more serious form than anticipated, this SAE should be considered a SUSAR.

8.4.9.2 Methods for eliciting adverse events

Adverse Events will be collected based on the Investigators' and other study staff's reporting as well as adverse events spontaneously reported by Subjects verbally and/or in questionnaires. All AEs, serious and non-serious, will be recorded in the eCRFs.

The following evaluations are to be done by the Investigator in connection with the AE:

- type of event
- seriousness
- degree of severity
- duration (start end)
- action taken
- causality with investigational product
- outcome of the adverse event

For AE reporting purposes no distinction should be made between the study product and any reference/comparator product.

For the purposes of this study, the monitoring period for AEs extends from the signature of the ICF by the subject until the collection of the last blood sample of the study. From screening to the first product administration of the product familiarisation session, AEs will be recorded as screening events or as part of the medical history, as applicable. AEs occurring from the first product administration of the product familiarisation session to the product administration of period 1 will be recorded as product familiarisation session events. AEs occurring after the first product administration (i.e. after the familiarisation session) will be indicated as TEAEs in the clinical study report.

Subjects will be questioned on their health status at the beginning of each study period and before each departure from the clinical site. Open-ended questions will be asked.

During the study, all AEs spontaneously reported by the subject, observed by the clinical staff or elicited by general questioning will be recorded for all subjects and reported in the CRF.

If necessary, every effort will be made to obtain an adequate follow-up of the subjects. Should any subject choose to withdraw from the study, they will be advised of the safety precautions to be taken.

Any AE which remains unresolved as of the last visit will require an evaluation and follow-up until the AE has been resolved or a reasonable explanation for its persistence found or is deemed mild and safely resolving.

In the case of AEs deemed related to the product, every effort will be made to determine the final outcome.

8.4.9.3 Intensity/severity

It is an investigator's responsibility to ensure subjects experiencing AEs receive appropriate followup, treatment where required, and that every action is well documented.

- Mild means awareness of symptoms or signs, but easily tolerated (acceptable)
- Moderate means discomfort enough to interfere with usual activity (disturbing)

Severe means incapacity to work or to do usual activity (unacceptable)

8.4.9.4 Causality

The causal relationship between an AE and the IP is defined as follows:

Not Related: The AE is definitely caused by the subject's clinical state or the study procedure/conditions.

Unlikely Related: The temporal association between the AE and the product is such that the product is not likely to have any reasonable association with the AE.

Possibly Related: The AE follows a reasonable temporal sequence from the time of product use but could have been produced by the subject's clinical state or the study procedures/conditions.

Related: The AE follows a reasonable temporal sequence from the time of product use, abates upon discontinuation of the product and reappears when the product is reintroduced.

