8 INVESTIGATIONAL PLAN

8.1 Overall study design and schedule of events

This is a two centre, randomised, non-blinded, 8-product, 8-period crossover, single dose pharmacokinetic study, in which 36 healthy male or female adult users of smokeless nicotine products (subjects who use pouched snus should regularly use pouch weights of 0.6 g and above, and at least 7.5 mg nicotine/pouch) will be randomised in competitive recruitment manner to receive one of the study products during each study period. The 8 periods of product use and sampling will be scheduled during two admission periods of 4.5 days each. There is also option for subjects to perform the product use and sampling in one 8.5 days admission period. For subjects choosing the one 8.5 admission option, they will come to the clinic on day 1 and will then receive the 8 products and undergo PK sampling on days 2-9 after which the subject is discharged. For subjects choosing the two admission periods of 4.5 days, they will come to the clinic on day 1 and will then receive 4 of the 8 products and undergo PK sampling on days 2-5 after which the subject is

discharged. Subjects will return for a second admission on day 8 with PK dosing and PK sampling of the remaining 4 products on days 9-12.

To minimise the risk of dropouts during the study, it will be accepted for subjects to be discharged during the 8.5-day admission period, or one or both of the planned 4.5-day admission periods, to return for re-admission and the remaining dosing and sampling at a later date. This option will only be used if absolutely necessary to avoid subjects to dropout of the study.

Subjects will be aged 19-55 inclusive and judged to be healthy by pre-study screening. Subjects must have been using smokeless oral nicotine products daily for at least 6 months and must not be trying to quit or planning on quitting during the study period. Product use status will be confirmed with a urinary cotinine level of ≥ 100 ng/ml at screening.

Subject eligibility for this study will be determined at the screening visit and eligible subjects will be admitted to the clinical research unit (CRU) at least 13 hours prior to the first product administration. The screening visit will take place up to 28 days prior to the first admission for product administration and PK sampling.

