During or after the screening visit but prior to admission for the confinement period, the subjects will attend the clinic for a familiarisation session in which they will be given the highest nicotine strength product (Granit Vit Stark 13 mg/pouch). The purpose of this familiarisation session is to ensure the subject tolerates the product with the highest nicotine strength to avoid dropouts due to product intolerance during the PK sampling period. The subject will use the product in the same way they would normally use a smokeless snus product. There will be a 20 minutes duration of use of the product (from the time the subject places the product in their mouth until the time the subject removes the product from their mouth). Subjects who successfully complete this familiarisation session, i.e., those who are willing to use and show no intolerance to the test product, will be allowed to continue in the study. Subjects who already use Granit Vit Stark (13 mg nicotine/pouch) or snus of 13 mg nicotine/pouch or above do not need to attend the familiarisation session.

For each study period, subjects will abstain from all tobacco and nicotine usage for 12 hours prior to product administration. In addition, subjects will fast overnight (no food or drink except water), for a minimum of 8 hours prior to each product administration. In the morning of each study session, Subjects will receive a standardised light breakfast which will be consumed at least one hour before product administration. Subjects will then receive a single product for a fixed period of 60 minutes and undergo a 6-hour PK blood sample collection. For each study period, a total of 13 blood samples (4 mL per sample) will be collected for PK assessments. PK blood samples will be collected prior to product administration (-5 mins) and at 5, 10, 20, 40, 50, 60, 65, 75, 90, 120, 240 and 360 minutes following product administration.

Subjects are to be discharged from the clinic after the final 6-hour post-administration PK sample collection in each admission period following medical approval. However, they may be advised to stay at the clinical site for safety reasons, if judged necessary by the physician in charge. End of study procedures will be performed prior to discharge from the clinical site.

The duration of the clinical portion of this study per subject (excluding the screening period) is expected to be 10 days. The actual overall study duration may vary.

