8.3 Treatments

8.3.1 Identity of Study Products

The following products will be administered in the study as 60 minute single product administrations.

- 1) Swedish Snus (pouch) Granit Vit Stark with 13 mg/pouch nicotine
- 2) Lyft (Commercial product), 4 mg/pouch
- 3) Lyft (Commercial product), 10 mg/pouch
- 4) Lyft non-commercial (alginate removed), 10 mg/pouch
- 5) Lyft non-commercial (benzoic acid added), 4 mg/pouch
- 6) Lyft non-commercial (benzoic acid added), 10 mg/pouch
- 7) Lyft non-commercial (citric acid added), 10 mg/pouch
- 8) Lyft non-commercial (benzoic acid added, sweet base), 10 mg/pouch

All products will be provided by the sponsor.

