8.4.9.5 Reporting of SAEs

All SAEs must be reported to IRW by the Investigator immediately and not later than within 24 hours of knowledge of the event regardless of the time that may have elapsed from the time the event occurred to when the Investigator first learns of it. The preferred method of reporting is through the eCRF, but paper versions of the SAE forms are always available on site if for any reason the eCRF cannot be accessed. The completed paper SAE form should be sent to IRW either via email or fax.

The Initial Report should contain as much information as possible, but a minimum the following information:

- subject identification
- treatment specification (blinded information, if code not broken)
- adverse event diagnosis
- time specification for the medical event
- name of the original reporter

A Serious Adverse Event Report Form must also be completed, signed by the Investigator and submitted to IRW no later than five calendar days after the initial information was received (preferably through the eCRF). Apart from the information above, this Follow-up Report should also contain the following information:

- assessment of severity
- assessment of causality

Investigator shall immediately inform IRW in writing if any of the below occurs (by email to: [contact]):

- (i) any serious adverse event (SAE),
- (ii) any incident,
- (iii) any investigational medical device deficiency that might have led to a SAE,
- (iv) new findings/updates in relation to already reported events, and/or
- (v) any corrective measure.

which occur during the study. When reporting any of the above, the investigator shall provide IRW with details of the product used, the nature of the event/reaction, anonymised patient details, and the details of the person reporting the event/reaction.

SAEs should be reported to IRW even after the study has been finished, if, in the judgment of the Investigator, there might be an association between the event and the previous use of the study product(s) or as a result of the study procedures. The minimum post-study observation period is 5 working days after the Post-study telephone follow-up, but this period can be extended in case the Investigator believe it is necessary.

Only SAEs that are both unexpected and related to the study product(s), Suspected Unexpected Serious Adverse Reactions (SUSARs), are subject to expedited reporting.

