19.5 Labelling of Study Products

General Case (containing 8 sequentially numbered pouches (1-8)) FOR CLINICAL TRIAL USE ONLY **KEEP OUT OF REACH OF CHILDREN** Sponsor: British American Tobacco Contract Research Organisation: IRW Consulting AB [contact] Investigator: [Investigator name] Tel No.: [Investigator Tel No.] Dosage form and directions for use: Nicotine containing pouch for oral user under the upper lip for 60 minutes Quantity: 8 packages containing 1 pouch each **Treatment Sequence Code Number**: [xx] Trial Reference Code: BAT2119018 **Subject Number:** [*enter number*] Storage conditions: Room temperature Use before: MM/YY Primary Package (containing one numbered pouch (1-8)) FOR CLINICAL TRIAL USE ONLY **KEEP OUT OF REACH OF CHILDREN Sponsor**: British American Tobacco Contract Research Organisation: IRW Consulting AB [contact] **Investigator**: [Investigator name] **Tel No.**: [Investigator Tel No.]

Dosage form and directions for use: Nicotine containing pouch for oral user under the upper lip for 60 minutes **Quantity**: 1 pouch

Treatment Sequence Code Number: [xx]

Treatment Number: [1-8]

Trial Reference Code: BAT2119018 **Subject Number:** [*enter number*]

Storage conditions: Room temperature Use before: MM/YY

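### The causality category *Related* requires recurrence on re-use, which single-use dosing cannot show for seven of the eight products, and it conflicts with the protocol's other definitions of a related event

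*Protocol*

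**What the plan says.** Section 8.4.9.4 (Causality) opens with "The causal relationship between an AE and the IP is defined as follows" and gives four categories: *Not Related*, *Unlikely Related*, *Possibly Related* and *Related*. *Possibly Related* is for an event in plausible time order that the subject's own condition or the trial procedures might also explain. *Related* needs plausible time order and, in addition, that the event "abates upon discontinuation of the product and reappears when the product is reintroduced". The conditions are joined by 'and', and no exception is made for a product used once.

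On dosing, section 8.1 describes an "8-product, 8-period crossover, single dose pharmacokinetic study" in which subjects are randomised "to receive one of the study products during each study period". Section 8.3.1 says: "The following products will be administered in the study as 60 minute single product administrations". The label text in section 19.5 gives the supply per subject as "8 packages containing 1 pouch each". The one extra exposure is the 20-minute familiarisation session (sections 8.1 and 8.4.3), which uses product 1, the 13 mg snus. Subjects who already use snus at that strength or above may skip it, and subjects who show intolerance do not continue.

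Other sections define a causal event differently. Section 8.4.9.1.3 counts an event as an adverse reaction if the investigator and/or the sponsor sees a reasonable causal link. Section 8.4.9.1.5 asks for a suspicion that the product caused a serious event. Section 8.4.9.2 asks for extra effort to establish the outcome of events judged related. Section 8.4.9.5 limits expedited reporting: "Only SAEs that are both unexpected and related to the study product(s".

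**The concern.** A causality scale works only if the investigator can use each category on the data the trial produces. Here the top category depends on an observation that the dosing plan does not provide for. Take local irritation under the pouch that clears on removal and has no other plausible cause. It does not qualify as *Related*, because the same product is not given again, and *Possibly Related* describes it wrongly, because that category presupposes a possible alternative explanation. The investigator must either misclassify the event or set the definition aside, and two sites may resolve this differently.

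The word related also steers follow-up in section 8.4.9.2 and expedited reporting in section 8.4.9.5. The protocol does not say which of the four categories it covers.

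**Working it through.** No sample size, power or error-rate figure bears on this point. The check is a count of planned administrations, followed by a comparison of the definitions.

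**1. Administrations per product and subject.** There are 8 periods with 1 product each, so 8 × 1 = 8 PK administrations, one for each of the 8 products. The supply agrees: 8 packages × 1 pouch = 8 pouches, with none left over. Reintroductions = administrations − 1.

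| Product | Familiarisation | PK periods | Total | Reintroductions |
|---|---|---|---|---|
| 1, subject attended familiarisation | 1 | 1 | 2 | 1 |
| 1, subject exempt | 0 | 1 | 1 | 0 |
| 2 to 8, each | 0 | 1 | 1 | 0 |

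Re-admission under section 8.1 is for dosing still outstanding, and previous inclusion in the study is an exclusion criterion (8.2.2, no. 16). Neither route leads to a repeat.

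**2. Product 1 in subjects who attended.** The event must first appear at familiarisation, because one that first appears at the product 1 PK session has no later use of that product. It must also not amount to intolerance, or the subject does not continue. Little is left that could qualify.

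**3. Reading the investigational product as a class.** If any later pouch counted as reintroduction, an event first seen in period k would have 8 − k later PK administrations: 7 for period 1, falling to 0 for period 8. An event that ends participation (section 8.2.4.2) would have none, whatever its period. So even on this reading the condition fails for a first event in the last period and for every event that leads to withdrawal.

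**4. The definitions side by side.**

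| Section | Test applied | Recurrence needed? |
|---|---|---|
| 8.4.9.1.3, adverse reaction | Reasonable causal link, in the view of investigator and/or sponsor | No |
| 8.4.9.1.5, SUSAR | Suspected cause, serious, not expected | No |
| 8.4.9.4, *Related* | Time order, abatement and recurrence | Yes |
| 8.4.9.2, follow-up | Judged related | Not stated |
| 8.4.9.5, expedited reporting | Unexpected and related | Not stated |

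An event on products 2 to 8 can therefore be an adverse reaction under 8.4.9.1.3 and yet be barred from *Related* under 8.4.9.4. Which meaning governs the last two rows is left open.

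**The case against.** **The class reading.** The title page names the investigational product collectively as oral nicotine products, and section 5.2.1 treats nicotine as the only pharmacologically active ingredient. Products 2 to 8 look alike (8.3.2), and the randomisation code is normally withheld from study staff until database lock (8.3.5), so the assessor would usually not know which of them was in use. A later pouch could then pass for a reintroduction. This is workable, and it means that the count of zero for seven products holds only when causality is read per product. But the protocol does not state the class reading, the definition itself speaks of the product in the singular, and step 3 of the working shows that the reading still fails in part. It would also rest the causality of one formulation on recurrence with another.

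**Own-brand use.** Section 8.4.4 allows it between sessions, and it could by chance be one of the commercial products 2 or 3. That is not study administration and not a planned re-exposure.

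**Expedited reporting.** A reader might infer that no serious event on products 2 to 8 could ever trigger an expedited report. The document does not support this. Sections 8.4.9.1.3 and 8.4.9.1.5 offer a route without recurrence, the sentence in 8.4.9.5 itself refers to suspected reactions, and every SAE goes to the CRO within 24 hours whatever its causality.

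**Snus as comparator.** A reader might also infer that causality tables will favour the modern oral products, since only snus can reach *Related*. This is not shown either. The category is almost empty for snus as well, familiarisation events are recorded separately (8.4.9.2), and the protocol's safety summaries are descriptive with no planned comparison of causality between products.

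**Practical weight.** All adverse events are recorded, and no primary or secondary endpoint uses the category. That stands, and it limits the size of the problem.

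**Conclusion.** The point holds as a defect of definition. Read per product, which is the natural reading, *Related* cannot be reached within planned dosing for 7 of the 8 products. For the eighth it is open only to subjects who attended familiarisation and had a tolerated event there that later recurred. The number of exempt subjects is not given, so that share cannot be sized.

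Two consequences follow: clearly product-caused events are misfiled as *Possibly Related*, and the meaning of related in sections 8.4.9.2 and 8.4.9.5 is unclear because 8.4.9.4 conflicts with 8.4.9.1.3 and 8.4.9.1.5. The efficacy and PK conclusions are untouched. Neither a blocked expedited report nor a bias against snus is demonstrated. The correction should be made, since a stated rule misclassifies safety data and costs almost nothing to change.

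**What to change.** - In section 8.4.9.4, make reappearance on renewed use supporting evidence for *Related* instead of a necessary condition. One possible form is plausible time order with no reasonable explanation in the subject's condition or the trial procedures.
- Reconcile sections 8.4.9.1.3, 8.4.9.1.5, 8.4.9.4 and 8.4.9.5 so that one test of causality runs through them. Say whether causality is judged against the individual product or the class.
- State which categories count as related for SUSAR assessment, for the follow-up duty in section 8.4.9.2 and for the safety tables. The table grouping may sit in the SAP. The definition belongs in the protocol, because the investigator applies it when the event occurs.

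The cost is one revised definition, consistent wording in the linked sections and matching eCRF guidance, handled as a protocol amendment. No visit, sample or subject is added.
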